### 4.2.2 Safety in Hemodialysis Patients

A review of the aggregate safety data shows that CR845 was generally well tolerated in hemodialysis patients when administered after each dialysis session for up to 8 weeks at IV doses ranging from 0.5 mcg/kg to 6 mcg/kg. Although patients exposed to CR845 reported more adverse events compared with placebo patients, most events were mild or moderate in nature. Generally mild, transient paresthesias (facial tingling) and/or hypoesthesias (in different anatomic locations), mostly on the first week of dosing, as well as headache, dizziness, and somnolence, were the most frequently reported adverse events associated with CR845 administration. Of note, side effects (eg, dysphoria and hallucinations) commonly associated with centrally-acting kappa opioids were not reported in patients exposed to CR845. Consistent with its lack of affinity for mu-opioid receptors, CR845 did not cause euphoria or respiratory depression.

CR845-CLIN2101 evaluated the safety, pharmacokinetics, and efficacy of repeated IV doses of CR845 compared to placebo over an 8-week treatment period in 174 hemodialysis patients. As expected with patients on hemodialysis, a significant number of the reported serious adverse events (SAEs) were considered not treatment-related, but related to the disease and/or comorbid conditions. There were 31 (17.8%) of

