174 patients randomized and treated in the study who had treatment-emergent SAEs. Of the 31 SAE reports, 4 (9%) occurred in 45 placebo-treated patients and 27 (21%) in 129 CR845-treated patients. Only 1 SAE of mental status changes (moderate in severity) in a patient who received CR845 1.5 mcg/kg IV was considered by the Investigator to be probably related to study drug. However, based on the Sponsor's medical review, an alternate etiology of urgent/emergent hypertension offers a more plausible explanation for the acute change in mental status. There were 4 patient deaths (1 in placebo group, 1 in CR845 0.5 mcg/kg group, and 2 in CR845 1.5 mcg/kg group; 2.3% of the total study population) in the study, all of which were considered not related to the study drug. In patients with normal renal function, CR845 can cause free-water diuresis (aquaresis) and increased serum sodium. However, as would be expected in patients undergoing dialysis in whom there are few functioning nephrons, there was no evidence of aquaresis or significant increases in serum sodium concentrations. There were no adverse trends in clinical chemistry or hematology values (drawn pre-dialysis), including no apparent differences between the placebo and CR845 groups in serum sodium. There were no discernable differences between treatment groups in vital sign results. Of particular note, among patients receiving CR845, there was no apparent reduction in blood pressure or respiratory rate following dosing.

Adverse event summary tables can be found in the [Investigator's Brochure](#), with further details of the safety profile of CR845.

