### **Adverse Event Causality or Relatedness to the Study Drug**

Every effort should be made by the Investigator to explain each adverse event and assess its relationship, if any, to study drug. The Investigator should consider many factors, including, but not limited to, temporal association of the event and date/time of study drug, duration of study drug, medical/biologic plausibility, pharmacology and adverse event profile of study drug, medical history (past medical history, underlying disease, comorbidities, intercurrent illness), concomitant medications, medical judgment, dechallenge, rechallenge, drug interaction, other plausible causes, etc., to determine the causality assessment of an event.

The Investigator as well as the Sponsor will determine adverse event/SAE causality as ‘Related’ or ‘Not Related’ to study drug. Although there is no international consensus on how to define ‘Related’ and ‘Not Related,’ in general, an event is considered ‘Related’ if there is reasonable possibility that the event is related to study drug rather than to any other possible cause(s). Conversely, an event is considered ‘Not Related’ if there is reasonable possibility that the event is related to other factors than the study drug.

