### **Serious Adverse Event Notification, Documentation, and Reporting**

The Investigator will report an SAE within 24 hours of becoming aware of the event. An SAE Report Form will be completed regardless of relationship to the study drug. The initial report will not be delayed in order to obtain additional information. Any additional information will be reported as a follow-up to the initial report within 24 hours of collection.

Details for reporting and follow-up of SAEs are provided in the ISF.

In the event of any SAE (other than death) occurring after the last dose of study drug and prior to the Follow-up Visit, the patient will be instructed to contact the Investigator or designee immediately using the instructions provided on the ICF.

The Medical Monitor will review reported SAEs and may contact the Investigator directly for further information.

---

The Sponsor will comply with the applicable local regulatory requirements related to reporting of SAEs to the appropriate regulatory authorities in the countries and regions this study is conducted, while the Investigator and designated study personnel will comply with the applicable local regulatory requirements related to reporting of SAEs to the IRB/IEC and the Sponsor.

It is the responsibility of the Sponsor or designee to send all regulatory reports to the appropriate regulatory authorities. Adverse events that are serious, related to the study drug, and unexpected (per the [Investigator's Brochure](#)) will be reported to the regulatory authorities as specified in the Safety Management Plan.

For regulatory reporting purposes, the Sponsor can upgrade the Investigator's assessment (eg, from not related to related); however, Sponsor cannot downgrade the Investigator's assessment unless the Investigator determines that a re-assessment of causality is necessary. The Medical Monitor will review and comment on any upgrade made to a report. If there is any doubt concerning the relationship between study drug and the event, then the relationship should be considered to be related to study drug.

As applicable, the Sponsor will also notify other participating Investigator(s) of all IND Safety Reports to ensure prompt notification of significant new adverse events or risks with respect to study drug. This notification will occur as soon as possible and in compliance with country-specific regulations.

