Treatment-emergent adverse events will also be summarized by severity for each study period of the Double-blind Phase and by relationship to double-blind study drug for the Double-blind Period. If the severity and/or relationship to the study drug of an adverse event is missing, a worst-case scenario will be assumed (ie, the adverse event will be categorized as “severe” and/or “related” to the study drug). If a patient reports the same TEAE multiple times the event with the worst severity and the strongest relationship to study drug will be tabulated.

For each period of the Double-blind Phase, an overall summary table will be provided, presenting for each treatment group: the number and percentage of patients with an adverse event (both treatment and non-treatment emergent) during that period, a TEAE, serious TEAE, related TEAE, severe TEAE, TEAE leading to dose interruption, and TEAE leading to study drug discontinuation. This table will also include the number of events for each specific Preferred Term.

All adverse events will be listed in chronological order, including patient identifier, age, race, gender, a flag indicating whether the event was treatment-emergent, and all related event status information (start and stop dates, whether the event was ongoing, study day of onset, severity, seriousness, relationship to study medication, action taken with study treatment, and outcome). Separate listings will be generated for SAEs, deaths, and adverse events leading to study drug discontinuation. Additionally, a coding list of Preferred Terms and the verbatim text associated with them will be produced.

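### 'Related' and 'Not Related' are not complementary, so an event with both a plausible drug cause and a plausible comorbid cause meets 'Not Related', which for SAEs conflicts with the any-doubt rule

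*Protocol*

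**What the plan says.** Under Adverse Event Causality or Relatedness to the Study Drug (Section 6.5.4.1), the Investigator and the Sponsor "will determine adverse event/SAE causality as ‘Related’ or ‘Not Related’ to study drug". There is no intermediate category. After listing factors to weigh, the section gives two definitions, introduced as holding in general:

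- 'Related': "there is reasonable possibility that the event is related to study drug rather than to any other possible cause(s").
- 'Not Related': "there is reasonable possibility that the event is related to other factors than the study drug".

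Under Serious Adverse Event Notification, Documentation, and Reporting, in a paragraph about regulatory reporting, the protocol adds: "If there is any doubt concerning the relationship between study drug and the event, then the relationship should be considered to be related". No sentence says which rule takes precedence.

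Three later steps use the classification:

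- Section 8.8.2 summarises TEAEs "by relationship to double-blind study drug for the Double-blind Period" and counts related TEAEs in the overview table.
- Adverse Event Documentation and Follow-up continues follow-up beyond the patient's participation only for ongoing events assessed as related.
- The same subsection, and Definition of Adverse Events, make the SAE form for events up to 30 days after the last dose depend on the Investigator's judgement of 'Related'.

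**The concern.** With only two categories, an event should be 'Not Related' exactly when it is not 'Related'. Here the first definition asks whether the drug is the more reasonable explanation, while the second asks only whether another explanation is reasonable. An event with two plausible causes can satisfy the second without the drug having been excluded.

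Such events are to be expected in this trial. Section 4.2.2 reports that a significant number of SAEs in an earlier haemodialysis study "were considered not treatment-related, but related to the disease and/or comorbid conditions". The Structured Safety Evaluation (Section 6.5.4.2) looks for mental status change, falls and gait disturbance, and a history of these conditions is a stratification factor (Section 8.3). Some patients will therefore carry a ready alternative explanation for the very events being watched.

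At stake are the related-event counts, the follow-up and documentation steps that depend on relatedness, and consistency across approximately 95 sites that may apply one rule or the other.

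**Working it through.** No figure in the protocol is in question, so the check sets the rules side by side. Take the two questions an assessor can answer: is the drug a reasonable cause, and is something else a reasonable cause?

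| Drug plausible | Other cause plausible | 'Related' definition | 'Not Related' definition | Any-doubt rule |
|---|---|---|---|---|
| Yes | No | Met | Not met | Related |
| No | Yes | Not met | Met | No doubt, not invoked |
| Yes | Yes | Fails, or at best unsettled | Met | Related |
| No | No | Not met | Not met | Not settled |

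1. Rows one and two give no difficulty.
2. Row three is the defect. The comparison with other causes in the 'Related' definition excludes the event or leaves it open. The 'Not Related' definition is met outright. The any-doubt rule gives the opposite answer.
3. Row four meets neither definition, which confirms that the two are not complements.

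**Where the rules collide.** The any-doubt sentence sits in the SAE notification text. For an SAE in row three, both rules apply and disagree. For a non-serious event, only the causality definition clearly applies. There is then no contradiction, but the definition that remains is the faulty one.

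**What follows downstream.**

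- Related-TEAE summaries (Section 8.8.2): the worst-case default to related covers a missing relationship only. A row-three event recorded as 'Not Related' is not missing, so the default does not reach it.
- Follow-up after the last visit: this depends directly on the assessment as related.
- SAE forms: the related-only condition up to 30 days is itself in tension with the notification text, which requires a form whatever the relationship. If adverse events are captured in full to the Follow-up Visit, the condition matters only after it. On the planned double-blind schedule (Table 2), the last dose is on Day 82, End of Treatment is Day 85, and the Follow-up Visit is 7 to 10 days later:
  - Follow-up Visit: 85 + 7 = Day 92 to 85 + 10 = Day 95.
  - Time since last dose: 92 − 82 = 10 days to 95 − 82 = 13 days.
  - Remaining window: 30 − 13 = 17 days to 30 − 10 = 20 days.

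**Size.** The protocol gives no proportion of events with two plausible causes and no rule for how sites would split them. The direction follows from the wording; the amount does not.

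**The case against.** The best case for the text is that it is guidance and not an automatic rule. It acknowledges that no international consensus exists, speaks in general terms, and follows a multi-factor assessment covering timing, dechallenge, rechallenge, pharmacology and comorbidity. Because the second sentence is introduced as the converse of the first, both can be read as comparative: choose the more likely cause. This stands to a degree. A reader might infer that any possible alternative cause forces 'Not Related', and the protocol does not go that far. But even the comparative reading offers no rule for two comparably plausible causes, and for SAEs it still disagrees with resolving doubt towards related.

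Four other stronger readings are tempting and unsupported:

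- **That expedited reporting is weakened.** The any-doubt sentence stands in the regulatory reporting paragraph. There the Sponsor may upgrade causality and may not downgrade it unless the Investigator finds a re-assessment necessary, and the Medical Monitor reviews reported SAEs. This protection is substantial. It is framed for regulatory reporting, however, and nothing carries an upgrade into the Section 8.8.2 tables.
- **That SAEs would go undocumented generally.** All adverse events go on the eCRF whatever the causality, and the notification text requires an SAE form for every SAE. Beyond 30 days a broader test of possible relationship applies.
- **That the Phase 2 data show under-counting.** Section 4.2.2 states that of the SAE reports, "4 (9%) occurred in 45 placebo-treated patients and 27 (21%) in 129 CR845-treated patients", with one SAE judged probably related. It does not give the causality definition used, and a grade of 'probably' suggests a different scale from this one. The figures say nothing about the present rule.
- **That nearly every event in these patients has another cause.** Section 4.2.2 supports only a significant number of SAEs, and it describes paraesthesia, dizziness and somnolence as associated with CR845.

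**Conclusion.** The definitions need correcting. As written they are not complementary, an event with two plausible causes meets 'Not Related', and for SAEs this contradicts the any-doubt rule with no stated precedence. The likely result is fewer or inconsistently classified events in the related-TEAE summaries, in follow-up of related events after the last visit, and under the 30-day related-only SAE form condition. The size is unknown, so under-counting is a likely direction and not an established fact.

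The reach is limited. TEAEs, SAEs, discontinuations and deaths are tabulated by arm without regard to causality, the Structured Safety Evaluation has no causality filter, the DSMB sees unblinded safety results, and no safety hypothesis is tested. The comparison of the arms on safety therefore does not rest on these definitions.

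The conclusion assumes that investigators classify by the protocol text. The Investigator Site File, the Safety Management Plan and eCRF guidance are not at hand and may say more, so inconsistent site practice is a risk and not an observation.

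**What to change.** Reconcile the two subsections of Section 6.5.4.1:

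- Define 'Related' as a reasonable possibility that study drug caused or contributed to the event, and 'Not Related' as no such reasonable possibility.
- State that a plausible alternative cause does not by itself make an event 'Not Related'.
- State that the any-doubt rule applies to all adverse events, not only in SAE reporting.
- Reconcile the related-only SAE form condition with the requirement for a form whatever the relationship.

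The core change is two definition sentences plus short clarifications, matching eCRF guidance and a memo to sites. The statistical cost is that the related-event count may become slightly less favourable. All-causality tables do not change. If events have already been classified under the present wording, the date of the change should be recorded so that related-event counts before and after it can be read separately.

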### **Adverse Event Documentation and Follow-up**

All adverse events, including observed, elicited, or volunteered problems, complaints, or symptoms are to be recorded on the adverse event page in the patient’s eCRF from the

---

time the patient signs the ICF and until the Follow-up Visit/early termination, whether or not judged by the Investigator to be related to study drug. The need to capture this information is not dependent upon whether adverse events are related to study drug. Serious adverse events that occurred up to 30 days after the last dose of study drug need to be documented on an SAE Report Form if they are deemed by the Investigator to be “Related” to study drug.

Each adverse event is to be documented with a verbatim/reported term, start and stop date and time, severity, causal relationship to study drug, action taken with study drug, and outcome (resolved, resolved with sequelae, resolving, fatal, unknown). The Investigator must review new adverse events and the outcome of ongoing adverse events frequently throughout the study.

In addition to recording all adverse events (serious and non-serious) in the patient’s eCRF, all SAEs must also be documented on the SAE Report Form for the study.

The Investigator will follow all adverse events until they resolve, the Investigator assesses them to be stable, or the patient’s participation in the study ends, whichever comes first. In addition, the Investigator will follow all adverse events assessed as related to study drug that are ongoing at the time of the patient’s last visit, until they resolve or the Investigator assesses them as stable, even if the patient’s participation in the study has ended. Resolution of such events is to be documented in the patient’s record as appropriate.

It is anticipated that some patients may undergo procedures and/or experience events that are common in the study population under investigation, independent of study therapy. Preplanned procedures and procedures (eg, kidney transplant, catheter replacement) or events that are independent of study therapy, according to the Investigator’s assessment, will be documented as specified in the Safety Management Plan.

### **Serious Adverse Event Notification, Documentation, and Reporting**

The Investigator will report an SAE within 24 hours of becoming aware of the event. An SAE Report Form will be completed regardless of relationship to the study drug. The initial report will not be delayed in order to obtain additional information. Any additional information will be reported as a follow-up to the initial report within 24 hours of collection.

Details for reporting and follow-up of SAEs are provided in the ISF.

In the event of any SAE (other than death) occurring after the last dose of study drug and prior to the Follow-up Visit, the patient will be instructed to contact the Investigator or designee immediately using the instructions provided on the ICF.

The Medical Monitor will review reported SAEs and may contact the Investigator directly for further information.

---

The Sponsor will comply with the applicable local regulatory requirements related to reporting of SAEs to the appropriate regulatory authorities in the countries and regions this study is conducted, while the Investigator and designated study personnel will comply with the applicable local regulatory requirements related to reporting of SAEs to the IRB/IEC and the Sponsor.

It is the responsibility of the Sponsor or designee to send all regulatory reports to the appropriate regulatory authorities. Adverse events that are serious, related to the study drug, and unexpected (per the [Investigator's Brochure](#)) will be reported to the regulatory authorities as specified in the Safety Management Plan.

For regulatory reporting purposes, the Sponsor can upgrade the Investigator's assessment (eg, from not related to related); however, Sponsor cannot downgrade the Investigator's assessment unless the Investigator determines that a re-assessment of causality is necessary. The Medical Monitor will review and comment on any upgrade made to a report. If there is any doubt concerning the relationship between study drug and the event, then the relationship should be considered to be related to study drug.

As applicable, the Sponsor will also notify other participating Investigator(s) of all IND Safety Reports to ensure prompt notification of significant new adverse events or risks with respect to study drug. This notification will occur as soon as possible and in compliance with country-specific regulations.

Refer to the Safety Management Plan for further details about SAE reporting and processing. The Medical Monitor should be contacted by study sites requiring additional clarification on an SAE.

#### **6.5.4.2 Structured Safety Evaluation**

A weekly Structured Safety Evaluation will also be used during the Double-Blind Phase to proactively identify and monitor adverse events of special interest.

The Structured Safety Evaluation will be performed once during the Run-in Period and weekly (preferably on Wednesday/Thursday) during the Double-blind Treatment Period. The Structured Safety Evaluation will be performed by qualified study staff using a list of specific signs/symptoms, including mental status change, falls and gait disturbance.

#### **6.5.4.3 Physical Examination**

Physical examinations will include an examination of the heart, lungs, abdomen, extremities, and neurological and vascular systems. Clinically significant abnormalities or worsening findings observed after the first dose of study drug will be reported as treatment-emergent adverse events (TEAEs).

#### **6.5.4.4 Vital Signs**

Vital signs include sitting or semi-recumbent body temperature, heart rate, and blood pressure and will be measured prior to start of dialysis.

Measurements will be repeated if a value is out of the reference range due to a technical issue, considered abnormal for the patient, or for other medical concerns. Only the repeated measurement will be recorded.

In the event of a clinically significant change in blood pressure and/or heart rate, the Investigator and dialysis staff will evaluate and manage the patient per standard dialysis unit practices with knowledge of the patient’s typical blood pressure and heart rate excursions.

Heart rate will be collected at each dialysis; if clinically significant and outside the prespecified visits per schedule of events, the heart rate will be recorded on the relevant CRF page.

